#### **G. ADDITIONAL SAFEGUARDS IF ANY PARTICIPANTS WILL BE VULNERABLE**

The trained Project Director or GRAs will review the potential subject's medical record, and if there are no exclusions, the subject will be invited to enroll. The subject and the subject's LAR will be provided with an oral explanation of the nature of the study and study information, in writing. The information will include all elements required for informed consent, and will include all pertinent contact information as well as information about withdrawal from the study. If at any time the subject or LAR does not wish to continue to participate in the study, no additional interactions with the subject will take place, no follow-up data will be collected and that subject's data forms will be destroyed. The study staff will work closely with the staff of the ICUs, the nurse managers and medical directors to ensure that all eligible patients have an equal opportunity for inclusion.

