**Serious Outcomes: SIRS, VAE and HAIs.** We will obtain data from the subject's medical record to evaluate SIRS criteria (heart rate > 90, respiratory rate > 20 or PaCO2 < 32 mm Hg, WBC > 12,000 mm^3 or < 4000 mm^3 or > 10% bands, temperature > 38 °C or < 36 °C) prior to the first tooth brushing intervention and daily thereafter while tooth brushing interventions continue. We will also monitor the results of any blood cultures obtained for clinical purposes from our subjects during the study period in order to identify clinical bacteremia. TGH has a robust surveillance program for

identification of bacteremia, VAC (including VAP), and sepsis. We will obtain HAI surveillance data regarding all study subjects from the Hospital Epidemiologist, as well as collecting data from each subject's medical record regarding diagnoses of these conditions by the clinical providers. We will also calculate length of intubation and length of stay for all subjects.

Sample Description and Patient Factors. Data will be collected from the medical record on additional factors in order to provide a comprehensive description of the study sample and conduct an exploration of the influence of individual-level factors on tooth brushing benefit and risk. Demographic data will be collected on study admission, and include age, gender, race, ethnicity, and smoking status. Preexisting global oral health will be measured by DMFT (Decayed, Missing, and Filled Tooth) Index assessed at study admission. The DMFT is a classic instrument which is widely used in dental practice and research. The score is calculated by visually inspecting each tooth and adding the number of decayed teeth, absent teeth, and filled teeth. Scores can range from a score of 0 (all teeth present and without caries) to a score of 32 (every tooth evidencing dental disease through loss, active dental caries, or repaired dental disease). The summative score will be used in examination of the exploratory aim. Severity of illness will be documented on admission to the study using the Acute Physiology, Age, and Chronic Health Evaluation (APACHE III). The APACHE III total score may range from 0 to 299 and consists of the following sub-scores: vital sign/lab, pH/pCO2, neurological, age, and chronic health. Scoring is done using the worst values for the first ICU day.

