Specific Aim 1 is to evaluate the clinical equivalence (non-inferiority) of three tooth brushing frequencies on oral health (dental plaque and mucosal inflammation) in critically ill adults receiving mechanical ventilation. To evaluate non-inferiority, we will use data from subjects who have at least 2 days duration of mechanical ventilation and at least 2 days of their randomly assigned tooth brushing regimen. Recognizing variable length of hospital stay and intubation, we will determine as the primary outcome the maximum difference in dental plaque since baseline assessment at the time of intubation. Whereas we would expect balanced distribution of the specific post-admission day in which this maximum difference is achieved between the 3 treatment arms (e.g. day 4, day 5, etc.), timing of the assessment will be included as a covariate along with baseline dental plaque score. Analysis of covariance (ANCOVA) will be used to compare adjusted dental plaque scores between the 1 and 3 times daily tooth brushing regimens. The test for non-inferiority of the single daily brushing regimen will be based on the 95% confidence interval for the adjusted difference between the 2 groups. For this analysis, we define non-inferiority as a modest between-group effect size of 0.50 or less (i.e. modest to low treatment effect associated with tooth brushing 3 times daily). Thus, if the upper limit of the confidence interval for the effect size is <0.50, then the single daily brushing regimen will be considered non-inferior to the 3 times daily tooth brushing regimen. If the non-inferiority test is not supported, a secondary test of the 1 versus 2 times daily brushing regimens will be conducted. Using this strategy, a direct test of non-inferiority of 2 versus 3 times daily is not required (see Table 2).

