Specific Aim 2 is to quantify and compare the safety of three tooth brushing frequencies on serious adverse outcomes, including ventilator associated complications and clinically relevant healthcare-associated infections. For aim #2, a composite HAI endpoint will be constructed consisting of VAP, bacteremia, and sepsis. Since HAIs are anticipated to be rare events across the 3 tooth brushing regimens, no formal between-group statistical testing will be conducted. Instead, 95% confidence intervals will be calculated for the proportion of subjects with HAI in each treatment arm. In addition, using person days of observation (i.e. days since intubation), we will calculate incidence rates (IR) of HAI by treatment arm and then calculate the number needed to harm (NNH) using the single daily brushing regimen as the

reference group and the formulas:  $NNH_{21} = (1 / (IR_2 - IR_1))$  and  $NNH_{31} = (1 / (IR_3 - IR_1))$  where  $IR_n$  = observed incidence rate in each treatment arm. In the event that the formal test of non-inferiority fails for the single daily brushing regimen, we will define clinically-relevant “compromised” safety as an NNH of 100 per less. This would be interpreted as 100 individuals or less being treated with the multiple daily tooth brushing to develop an HAI that otherwise would not have occurred with the single daily brushing regimen.

Clinical recommendations defined *a priori* and developed from the analyses conducted for aims 1 and 2 will be developed as defined in Table 2.

Table 2. Application of study findings to tooth brushing frequency recommendations

Comparison Groups a	Non-Inferiority	NNH	Recommendation	Rationale
1 versus 3	Supported	N/A	1 time/day	1 time/day non-inferior and safe
1 versus 3	Not supported	$\geq 100$	3 times/day	1 time/day inferior, 3 times/day safe
1 versus 3	Not supported	$< 50$	1 time/day	1 time/day inferior, but 3 times/day safety concern
1 versus 3	Not supported	50 to 100	See 1 vs. 2	1 time/day inferior, but 3 times/day safety concern
1 versus 2 b	Supported	N/A	1 time/day	1 time/day non-inferior and safe
1 versus 2 b	Not supported	$\geq 100$	2 times/day	1 time/day inferior, 2 times/day safe
1 versus 2 b	Not supported	$< 100$	1 times/day	1 time/day inferior, but 2 times/day safety concern

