## **XII. DATA AND SAFETY MONITORING**

A Data and Safety Monitoring Plan (DSMP) will be implemented for the purpose of monitoring safety of the study, including but not limited to review of adverse events. Monthly DSMP meetings will include the PI, project director, biostatistician, data manager, and GRAs. The DSMP meetings will include review of all safety and adverse events data. Summary reports of data will be prepared by the data manager and project director. DSMP reports will consist of protocol compliance with inclusion/exclusion criteria, gender and minority and adverse events review. Written minutes of DSMB meetings with summaries of adverse events will be forwarded to the IRB and NIH as part of the annual reporting process. Research staff will report any adverse event immediately to the PI. Enrollment, study fidelity, and safety data will be reviewed regularly at study team monthly meetings. All adverse events will be reported to the TGH and USF IRBs, and the NIH, following institutional and NIH guidelines. We believe that the protocol is low risk and that this should be adequate.

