### F. RISK REDUCTION

The intervention will be interspersed with the care team's activities, and at no time will the study personnel delay or interfere with clinical care; if the needs and activities of providers are such that the study personnel are unable to access

the subject to provide interventions, the subject will be withdrawn from the study. At all times we will place the subject's need for medical treatment, and avoidance with interference with treatment, foremost.

In order to reduce risks to privacy of individuals or confidentiality of data, we will not include personally identifiable data in the database files. All computers and data files will be password protected, and data will be stored on the University server, with access only to study personnel, under the direct supervision of [name]. Because these subjects are receiving clinical care in the hospital, the attending clinical medical providers will be promptly informed of any adverse effects to the subjects; if an adverse event occurs, necessary interventions will be determined and delivered by the clinical providers.

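### Destroying the data forms of subjects who withdraw discards infection events and person-days already observed for Aim 2, and the loss cannot be reversed

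*Combined protocol and SAP*

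**What the plan says.** The rule is in section XVI.G (Additional Safeguards). Its trigger is broad: "If at any time the subject or LAR does not wish to continue to participate in the study". Its consequence is that "no follow-up data will be collected and that subject's data forms will be destroyed". No distinction is made between data still to be collected and data already in hand, and no safety or HAI outcome is exempted.

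Section XVI.F adds a second route, started by the study. If staff cannot reach "the subject to provide interventions, the subject will be withdrawn from the study". It does not say what happens to those subjects' data.

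For Aim 2, section XI states that "95% confidence intervals will be calculated for the proportion of subjects with HAI in each treatment arm". It then forms incidence rates over person-days since intubation and takes the NNH as the reciprocal of the rate difference from the once-daily arm. No analysis population is named for Aim 2, and handling of withdrawn subjects is not described. For Aim 1 the population is already restricted: "we will use data from subjects who have at least 2 days duration of mechanical ventilation", with at least 2 days of the assigned regimen as well.

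On sources, Key Variables and Measurement says "We will obtain HAI surveillance data regarding all study subjects from the Hospital Epidemiologist", with provider diagnoses taken from the medical record. Section XII says "The DSMP meetings will include review of all safety and adverse events data".

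**The concern.** Ending contact and new collection respects a withdrawal. Destroying records gathered while consent was valid is a further step, and the protocol gives no reason for it.

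Withdrawal is a realistic event here. Consent usually comes from a representative. Willingness is reassessed throughout, and subjects are approached for their own consent as they improve. A subject who regains capacity on day 4 or 5 and declines would lose the whole record, so the loss may follow clinical course. It could also follow arm: a session takes about 15 minutes, so the arms differ by roughly 15, 30 and 45 minutes a day.

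Aim 2 is a primary aim built on events that the plan itself expects to be rare, and its NNH selects the recommendation in Table 2 when non-inferiority is not supported. If withdrawal is unrelated to outcome and arm, dropping events together with their person-days costs precision only. If it is related, the rates are biased, and nothing in the retained study data would show by how much.

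**Working it through.** **Plan's own figures.** The sample size reproduces. With margin 0.50 SD, true difference 0, one-sided alpha 0.10 and power 95%, n = 2 × (1.2816 + 1.6449)² / 0.50² = 68.5, so 69 per group. Then 3 × 69 = 207, and 207 / 0.60 = 345, or 115 per arm with equal allocation. The HAI precision statement also reproduces: an exact interval at 0.05 × 69 = 3.45 events is 0.012 to 0.131, against the stated 0.01 to 0.13.

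**Expected loss.** The documents give no withdrawal rate, so I assume 5%, with a range of 2% to 15%. The 5% HAI proportion is the plan's illustration.

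- At 5% withdrawal: 115 × 0.05 = 5.75 records per arm, and 5.75 × 0.05 = 0.29 events per arm.
- At 2%: 2.3 records and 0.12 events per arm. At 15%: 17.25 records and 0.86 events per arm.
- If HAI risk were 20% (assumed): 0.46 to 3.45 events per arm over the same range.

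With 5% withdrawal unrelated to HAI, the chance that a given arm loses at least one event is 1 − 0.95^5.75 = 0.26. The chance of losing two or more is about 0.03 (Poisson, mean 0.2875).

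**What one event does to the NNH.** The formula in section XI uses rates per person-day, so NNH cut-points of 100 and 50 are rate differences of 0.01 and 0.02, or 1 and 2 per 100 person-days. Observed days per subject are not given; I take 3, 5 and 7.

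| Days per subject | Person-days per arm | One event moves the rate by (per 100 person-days) | Excess events for NNH = 100 |
|---|---|---|---|
| 3 | 345 | 0.29 | 3.45 |
| 5 | 575 | 0.17 | 5.75 |
| 7 | 805 | 0.12 | 8.05 |

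Two illustrations at 5 days per subject, with 6 events in the once-daily arm (115 × 0.05 = 5.75, rounded):

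- Near a cut-point: 12 versus 6 events gives 575 / 6 = 95.8. Removing one event record and its 5 days from the higher arm gives 1 / (11/570 − 6/575) = 112.8. The 1-versus-3 result moves from the row that defers to the 1-versus-2 comparison to the row for an NNH of 100 or more.
- Away from a cut-point: 10 versus 6 gives 575 / 4 = 143.8. Removing one record gives 1 / (9/570 − 6/575) = 186.8, and the row does not change.

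On the subject-proportion scale, one event is 1/115 = 0.87 percentage points. There, 8/115 versus 6/115 gives NNH 57.5, and 7/114 versus 6/115 gives 108. That makes the result look far more fragile, but it is not the scale of the plan's formula.

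**Aim 1.** If 5% withdrawal came on top of the 40% allowance, n per arm would be 69 − 5.75 = 63.25 and power would fall from 0.951 to 0.937. At 2% and 15% it would be 0.946 and 0.896. The allowance includes missing data, so it may already absorb some of this.

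**The case against.** The opposing case is strong on consequences, and much of it stands. A reader might infer any of the following, but the documents do not support them.

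- *An all-randomised analysis becomes impossible.* Two master copies of the randomisation list are kept (Procedures), so denominators, assigned arms and best- and worst-case bounds survive. What is lost is an analysis of observed outcomes for everyone randomised. Aim 1 was never planned as all-randomised.
- *Participant flow cannot be reported.* Nothing prevents recording that a numbered subject withdrew.
- *Safety events vanish, contradicting section XII.* Adverse events go to the investigator at once, are reviewed monthly, and are reported to both IRBs and NIH. Later destruction of forms does not undo that review. HAI outcomes also originate in hospital records. The rule names data forms; whether server files, images and fluid samples are included is not stated.
- *Losing one or two events will typically change the recommendation.* On the person-day scale it does so only near a cut-point, and the NNH enters Table 2 only if non-inferiority is not supported.
- *Withdrawal will differ by arm.* This is plausible but not shown. Most subjects are sedated at first, and data collectors are blinded to arm.

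There is also an ethical argument. The rule is a safeguard for vulnerable people, mostly enrolled by proxy, and keeping data from someone who regains capacity and declines is a real trade-off. The consent pages were not available, so any promise made there cannot be assessed.

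These points limit the size of the concern without removing it. The surviving records are not planned as an analysis source for withdrawn subjects.

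**Conclusion.** The concern holds in a limited form. Followed as written, section XVI.G removes validly collected HAI events and person-days from Aim 2, possibly in relation to clinical course or arm, and irreversibly. The main harm is to Aim 2; for Aim 1 the rule adds to an existing exclusion.

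The likely size is modest: about 0.3 events per arm at an assumed 5% withdrawal and the plan's 5% HAI proportion, and 0.1 to 0.9 for withdrawal of 2% to 15%. A single lost event can alter the Table 2 row, but only close to a cut-point and after a failed non-inferiority test. These figures rest on an assumed withdrawal rate, equal arms of 115 and 3 to 7 observed days per subject. The case for changing the rule is that the loss is avoidable and cannot be repaired afterwards, not that it is expected to be large.

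**What to change.** Amend section XVI.G and the matching consent wording, with IRB approval:

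- At withdrawal, contact, study procedures and new data collection end, as now. Data collected up to that date are kept and analysed by assigned arm. At a minimum this covers assigned arm, withdrawal date, person-days, and HAI and other safety outcomes.
- Data are destroyed only on the explicit request of the subject or representative. State whether such a request reaches server files, images and stored samples.
- State how data are handled for subjects withdrawn under section XVI.F because staff could not gain access.
- In section XI, state how withdrawn subjects enter the Aim 2 proportions and rates, and report the number and timing of withdrawals by arm, including any destruction requests.

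The cost is an IRB amendment and revised wording; no sample size, visit or procedure changes. The downside is that pre-withdrawal data are retained for subjects who regain capacity and decline, unless they ask for destruction. The change should be made before withdrawals occur, because destroyed records cannot be recovered.

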#### **H. CONFIDENTIALITY**

Each participant will be assigned an arbitrary code number to ensure anonymity of the research data, and all research data will be maintained in locked file cabinets under the direct supervision of the PI. Study information obtained will be kept strictly confidential, and it will not be possible to identify any participant from the reports of publications that may result from this research.

#### **I. PRIVACY**

All interactions with subjects and LARs will be conducted in the subject's hospital room or a private area of the ICU. The information obtained will be kept strictly confidential, and it will not be possible to identify any participant from the reports of publications that may result from this research. Each participant will be assigned an arbitrary code number to ensure anonymity of the research data, and all research data will be maintained in locked file cabinets under the direct supervision of the PI.

#### **J. RISK/BENEFIT**

The risks are minimal, because tooth brushing is a commonly performed procedure, which is currently used in the clinical setting without any assessment of risk.

Benefits to participation include potential improvement in oral health, as all subjects receive the standardized tooth brushing protocol at scheduled intervals. Control of dental plaque and reduction of oral inflammation are likely to improve patient comfort, and may reduce systemic sequelae related to a nidus of inflammation in the mouth.

This study will result in a determination of the optimal frequency of tooth brushing in mechanically ventilated adults to maximize oral health benefits while minimizing systemic risks, thus optimizing patient outcomes as well as nursing effort. We anticipate that this knowledge will have immediate impact on bedside nursing practice, and that specific evidence-based guidance for oral care in mechanically ventilated adults will improve control of dental plaque and mucosal inflammation, with added benefit of improving patient comfort.

#### **K. COMPENSATION PLAN**

No subject compensation is planned.

#### **L. CONSENT ISSUES**

##### **1. CONSENT PROCESS**

The Principal Investigator, Project Director or GRAs will recruit and enroll subjects. Study personnel will review each subject's medical record and confirm with the medical staff that the subject is age 18 or older and if there are no barriers to inclusion, the potential subject will be approached for enrollment. The subject's ability to participate in consent processes will be evaluated as previously described. The subject and the subject's legally authorized

representative (LAR) will be provided with an oral explanation of the nature of the study and study information in writing. In any instance where the potential subject's ability to comprehend and communicate his/her desires is in question, we will seek consent for continued participation from the LAR and will invite the research subject to provide his/her assent. Further, subject's willingness to continue participation will be assessed on an ongoing basis throughout the project. We will follow the USF and TGH IRB Policies and Procedures and Florida Code.

## 2. SPECIAL CONSENT PROVISIONS

We will obtain consent for ongoing study participation from the LAR for subjects unable to provide consent because of critical illness, emergent intubation and inability to communicate.

### 3. *ASSENT PROCESS for decisionally impaired subjects.*

We will evaluate the potential subject's level of orientation and response to our discussions of the study on a daily basis, and if the potential subject is able to respond in a manner that is clearly understandable, we will use the potential subject's own consent to continue participation. However, in any instance where the potential subject's ability to comprehend and communicate his/her desires is in question, we will seek consent for continued participation from the LAR and will invite the research subject to provide his/her assent. Further, subject's willingness to continue participation will be assessed on an ongoing basis throughout the project.

